3.3 Sample Size and Power Considerations

For the primary estimand, the sample size of 159 is expected to provide adequate power for the comparisons between MT-7117 and placebo for change from baseline in the average daily sunlight exposure time (minutes) to first prodromal symptom associated with sunlight exposure between 1 hour post sunrise and 1 hour pre-sunset at Week 26 based on the MT-7117-A01 study. The calculation of sample size assumes a 2-sided alpha level of 0.05 and a 20% dropout rate up to Week 26. The sample size of 42 completers per treatment group will provide 91% and 79% power to detect an effect size of 0.72 and 0.66 in the average daily time (minutes) to first prodromal symptom associated with sunlight exposure between 1 hour post sunrise and 1 hour pre-sunset at Week 26 (ie, an absolute treatment difference of 57 mins between MT-7117 [REDACTED] [REDACTED] vs placebo, 52 mins between MT-7117 [REDACTED] [REDACTED] vs placebo, and a standard deviation [SD] of 79.3 mins). The sample size of 42 completers was calculated by SAS simulation using the fixed sequence testing procedure in order to confirm the power affected by multiplicity adjustment in treatment comparison for primary endpoint. Taking into account for a 20% dropout rate up to Week 26, total sample size of 159 was calculated.

Due to the rapid enrollment rate in the last few months of the enrollment period after COVID-

19 restrictions were lifted in many countries, a total of 184 subjects were enrolled.

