2. The mean intensity on an 11-point Likert scale of the subject's prodromal symptoms in a day is calculated. It is the average of all the intensity on an 11-point Likert scale of the subject's sunlight-induced prodromal symptoms in the day. The average daily mean intensity on an 11-point Likert scale of the subject's prodromal symptoms at a time point (Baseline, Week 2, 4, 6, 8, 10, 12, 14, 16, ..., 24, 26, 39, 52 and Follow-up for each period) is the average of the daily mean intensity of qualified days in the corresponding 14 day window. At least 1 day diary data is required for each 14 day window to be qualified for this calculation.

The following endpoint is derived when applying the similar rule as above.

- The average daily mean intensity of the subject's phototoxic reactions (associated with sun exposure) on an 11-point Likert scale

7.2.2.3.3. The average daily duration of sunlight exposure regardless of time of day without prodromal symptoms

The following is the procedure to calculate the average daily mean duration of sunlight exposure regardless of time of day without prodromal symptoms. The analysis windows are defined in the Table 2

1. Step 1 in section 7.2.2.3.1 will not be applied.
2. A diary day is qualified if the subject had non-zero duration of sunlight exposure in the day.
3. The duration of sunlight exposure without prodromal symptoms in a day is calculated. It is the sum of the duration of sunlight exposure time deducting the prodromal symptom or phototoxic reaction presenting time covered in each period.
4. Step 4 to 5 in section 7.2.2.3.1 will be applied.

7.2.2.3.4. Total number of sunlight-induced pain events defined as prodromal symptoms (burning, tingling, itching, or stinging) with pain rating of 1-10 on the Likert scale

The following is the procedure to calculate this endpoint.

1. If a subject had sunlight exposure with any prodromal symptom with pain rating of 1-10 on the Likert scale in a day, the sum of the number of events for the day is used as the number of sunlight-induced pain events in the day.
2. The sum of the number of the above events in each day during the 26-week DBT or DBE period (from Baseline date to Week 26 or from Week 26 to Week 52) is calculated as this endpoint.

The following endpoint is derived when applying the similar rule as above.

- Total number of sunlight-induced non-prodrome, phototoxic reactions
- Total number of sunlight-induced pain events defined as phototoxic events

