Patients with the first missing value occurring at Week 2 (“W2”) will have their missing Week 2 value replaced by an imputed value from a regression model with [REDACTED]

[REDACTED] and the baseline value (BASE) as explanatory variables. In the next step, patients with their Week 4 (“W4”) value missing will have their missing Week 4 value replaced by an imputed value from a regression model with baseline average daily first to prodromal symptoms and the Week 2 value as explanatory variables. Similar procedure will be used to replace the missing values at week 4, 6, 8 and 10 etc. [REDACTED]

[figure not shown]
[REDACTED] If the imputed value is less than 0 and then the value will be replaced with 0.

The following SAS code for the missing data imputation at Week 26 will be used to make the imputation with the MNAR assumption:

[REDACTED]

- Step 3: The imputed dataset (IMPUTED) generated with the approach described above do contain only non-missing values. MMRM model similar to that described for the primary analysis will thus be run on each of the 100 generated imputed datasets and the differences between the treatment groups at Week 26 will be estimated (and export to data 'ESTIMATES'). Finally, the MIANALYZE procedure in SAS will be applied to combine the results from these analyses to derive an overall estimate of the treatment differences at W26. In addition to the estimates, corresponding 95% confidence intervals and p-values will be calculated.

The following example SAS code will be used:

(3) Non-parametric analysis

Non-parametric analysis will be performed in order to confirm the robustness for the above parametric model. The change from baseline in average daily time (minutes) to first prodromal symptom associated with exposure to sunlight between 1 hour post sunrise and 1 hour pre-sunset at each visit (Weeks 2, 4,..., 24, and 26) from two treatments being compared will enter the corresponding analysis. The point estimates and two-sided 95% confidence intervals for the difference between the treatment groups will be obtained using the Hodges-Lehman estimator corresponding to Wilcoxon's rank sum test. The paired comparison between each MT-7117 arm with placebo will also be performed using this non-parametric analysis method. This non-parametric analysis will be performed with multiple imputation (MI) method in the following steps, assuming missing at random.

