The following endpoint will be listed and summarized by treatment and planned time point using descriptive statistics. The value of melanin density, change from baseline and % change from baseline in melanin density at each visit by skin segments and average of 6 skin segments will be plotted by treatment. The average of 6 skin segments for the melanin density and for the change from baseline in melanin density at each visit, will be analysed using MMRM model similar to the analyses for the primary endpoint. A subgroup analysis by region (North America, Europe, Japan, Australia), by Fitzpatrick scale test category (I-II or III-VI), by Melanin density at BL (\geq Median, $<$ Median) and by the [REDACTED] will be done.

- Change from baseline and % change from baseline in melanin density at each visit by skin segments. Average of 6 skin segments for the change from baseline and % change from baseline in melanin density at each visit.

The following endpoints will be analysed using either ANCOVA or ANOVA model. The ANCOVA model will include the treatment group, randomization strata as fixed factors together with continuous covariate terms for the corresponding baseline values except for the below total

time endpoints.

- Change from baseline for in-clinic sunlight exposure time (minutes) to the first prodromal symptoms or end of test, whichever comes first.
- Total time (hours) during the 26-week double-blind treatment period in duration of sunlight exposure between 1 hour post sunrise and 1 hour pre-sunset without prodromal symptoms.
- Total time (hours) during the 26-week double-blind treatment period in duration of sunlight exposure between 1 hour post sunrise and 1 hour pre-sunset without prodromal symptom with the severity of greater than 0 on 11-point Likert scale and without phototoxic reactions (pain-free time hours).
- Change from baseline in average daily duration of sunlight exposure regardless of time of day without prodromal symptoms assessed at Week 26.

The following endpoints will be summarized using descriptive statistics and Wilcoxon's rank sum test.

- Total number of days subject is exposed to sunlight for any duration without prodromal symptoms during 26-week double-blind treatment period.

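### The exploratory sun-exposure analyses in SAP 8.2.3 leave some precision unused: no continuous baseline covariate for total hours, a single-visit model for daily duration, and unstratified rank tests for day counts

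*SAP*

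**What the plan says.** Sunlight exposure duration is the first exploratory objective (SAP 2.1). SAP 8.2.3 handles the endpoints that bear on it in three ways.

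- **Total hours** (symptom-free and pain-free, over 26 weeks): ANCOVA or ANOVA, with the choice left open. The ANCOVA has treatment and randomisation strata, "together with continuous covariate terms for the corresponding baseline values except for the below total" time endpoints.
- **Daily duration**: "Change from baseline in average daily duration of sunlight exposure regardless of time of day without prodromal symptoms assessed at Week 26" is in the same ANCOVA/ANOVA list. It keeps its baseline covariate if ANCOVA is used, but enters at one visit. Its derivation in SAP 7.2.2.3.3 says "Step 4 to 5 in section 7.2.2.3.1 will be applied", and step 4 yields a value at baseline and at every two-week point to Week 26. No missing-data rule is given.
- **Day counts**: descriptive statistics and a Wilcoxon rank sum test, with no strata named.

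In the same section, other diary change endpoints, such as daily duration of prodromal symptoms, get the primary-type MMRM with their own baseline covariate. SAP 8.1.5 lists region and categorised baseline time to first prodrome as the randomisation stratification factors. Separately, in the non-parametric sensitivity analysis of the primary endpoint (SAP 8.2.1), estimates and intervals "will be obtained using the Hodges-Lehman estimator corresponding to" the Wilcoxon test, again without strata.

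**The concern.** The trial already holds data that would sharpen these comparisons, and the SAP gives no reason for setting them aside.

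The baseline diary gives, per day, the quantity that the total-hours endpoints sum over 26 weeks. Daily duration exists at 13 post-baseline windows, but a Week 26 model without imputation uses none of the first 12. It drops any subject without a qualifying Week 26 diary day. That loses precision and needs a stronger missing-data assumption than the MMRM does. Rank tests that ignore prognostic strata are conservative.

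At stake are the width of the intervals for the exploratory exposure endpoints and, for daily duration, a possible bias if loss of diary data differs by arm. Protocol 5.2 reports adverse events leading to discontinuation of 14.3% against 0% on placebo in one Phase 2 arm, so unequal discontinuation is plausible. That figure does not show that dropout follows poor exposure values.

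**Working it through.** **The plan's own figures (SAP 3.3).** These concern the primary endpoint: "The calculation of sample size assumes a 2-sided alpha level of 0.05 and a 20% dropout rate up to Week 26", and "The sample size of 42 completers per treatment group will provide 91% and 79% power to detect an effect size of 0.72 and 0.66".
- Effect sizes: 57/79.3 = 0.72 and 52/79.3 = 0.66.
- Power with 42 per arm: for 57 min, 90.9% (normal) or 90.2% (t). For 52 min as a single test, 84% to 85%. Both tests in fixed sequence succeed in 79.0% to 79.5% of simulated trials.
- 42/0.8 = 52.5, rounded up to 53; 53 × 3 = 159.

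The stated design reproduces. It supplies only a scale here, because the documents give no SD, effect or correlation for the exploratory endpoints. With 184 randomised, 184/3 ≈ 61 per arm, and 61.3 × 0.8 ≈ 49 with Week 26 data at 20% dropout. The power figures below assume an illustrative effect of 0.5 SD.

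**(a) Total hours.** Let ρ be the correlation of baseline daily exposure with the 26-week total. Residual variance, as a share of the total, is 1 with no adjustment, 1 − (2/π)ρ² with a stratum that splits this baseline at its median, and 1 − ρ² with the continuous covariate. The median split is an assumption: the actual stratum is on time to prodrome and its cut-off is redacted.

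| ρ | strata only | covariate | ratio | extra subjects v strata-only | extra subjects v plain ANOVA | power, 49/arm, strata-only to covariate |
|---|---|---|---|---|---|---|
| 0.3 | 0.943 | 0.910 | 0.965 | 3.6% | 10% | 72% to 74% |
| 0.5 | 0.841 | 0.750 | 0.892 | 12% | 33% | 77% to 82% |
| 0.7 | 0.688 | 0.510 | 0.741 | 35% | 96% | 85% to 93% |

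**(b) Daily duration, precision.** With monotone dropout d and correlation ρ between an earlier visit and Week 26, the variance ratio of the likelihood analysis to the Week-26-only analysis is 1 − dρ². At d = 0.2 and ρ = 0.5 / 0.7 / 0.8 it is 0.950 / 0.902 / 0.872. Effective n per arm rises from 48.8 to 51.4 / 54.1 / 56.0, and power from 69.5% to 72% / 74% / 75%.

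**(b) Daily duration, bias.** Simulation with 61 per arm, SD 79.3, true difference 57 min (scale borrowed from the primary endpoint) and about 20% dropout. Dropout depended on a poor earlier value on active and was random on placebo.
- Week 26 ANCOVA with its baseline covariate: bias roughly +3 to +5 min, favouring active.
- Likelihood analysis that also uses the earlier visit: 0.4 min or less.
- Same dropout mechanism in both arms: about zero.

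**(c) Day counts.** Simulation with 61 per arm, four balanced strata (assumed) and effect 0.5 SD.

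| variance explained by strata | plain Wilcoxon, rejection under the null | power, plain | power, van Elteren |
|---|---|---|---|
| 5% | 5.0% | 77% | 78% |
| 10% | 3.7% | 76% | 79% |
| 20% | 3.5% | 78% | 84% |
| 30% | 2.0% | 79% | 89% |

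The van Elteren test rejected in 4.6% to 5.7% of null trials.

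**The case against.** The strongest reply is that the planned analyses are valid, follow Protocol 14.3.2.2, and serve exploratory endpoints. That stands, and it limits the weight of the point. It also answers several stronger readings.

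- *A reader might infer that total hours are analysed with no baseline information.* The SAP exempts only the continuous term. The ANCOVA keeps the strata, one of which is categorised baseline time to prodrome. The 33% to 96% gains at ρ = 0.5 to 0.7 apply only if plain ANOVA without strata were chosen.
- *A reader might infer that the Week 26 analysis is completers-only.* SAP 8.2 puts efficacy endpoints under the treatment-policy estimand, subjects off drug are encouraged to stay, and one diary day qualifies a window. Off-drug subjects with diary data remain.
- *A reader might take the bias to be +8 to +11 min.* That needs an analysis without the baseline covariate as well as dropout tied to outcome in one arm only. The SAP's ANCOVA for this endpoint includes the covariate.
- *A reader might think the plain rank tests invalid.* They are conservative, not inflated. The Hodges-Lehmann analysis belongs to the primary endpoint's sensitivity set, works on change from baseline, and imputes with strata and baseline in the model.

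The MMRM is also not free of cost. Thirteen visits give 13 × 14/2 = 91 unstructured covariance parameters, and SAP 8.2.1 itself anticipates non-convergence.

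The reply does not explain why available baseline and repeated values go unused when sister endpoints in the same section use theirs.

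**Conclusion.** The point holds as a modest improvement to exploratory analyses. Omitting the continuous baseline for total hours costs the equivalent of about 4% to 35% of sample size against strata-only ANCOVA (assumed ρ 0.3 to 0.7, median-split stratum). The Week-26-only model for daily duration forgoes a variance cut of roughly 5% to 13% (20% dropout, assumed ρ 0.5 to 0.8). It is open to a bias of about +3 to +5 min only if dropout follows earlier values in the active arms and not on placebo. The rank-test part is minor: 0 to 10 power points, depending on how prognostic the strata are.

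The text of the SAP is clear on all three parts. The sizes are illustrative, since no correlation, SD or effect for these endpoints is in the documents. A reader might infer a threat to the trial's main result. There is none: total hours, daily duration and the day counts are outside H1 to H12, and the rank analysis of the primary endpoint is a sensitivity check, so neither the primary conclusion nor the type I error changes.

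**What to change.** **(a)** Name ANCOVA, not a choice of models, for the two total-hours endpoints. Include treatment, randomisation strata, and baseline average daily symptom-free (or pain-free) exposure from the 14-day baseline diary.

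**(b)** Analyse daily symptom-free duration with the primary-type MMRM over Weeks 2 to 26, with its own baseline covariate, and report the Week 26 contrast. Apply the covariance fallback order of SAP 8.2.1 if the unstructured model does not converge.

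**(c)** Optional: use van Elteren tests for the day counts, stratified by randomisation stratum. The Hodges-Lehmann sensitivity analysis of the primary endpoint could likewise use changes aligned by stratum. State which stratum source is used, because SAP 6.3 reports mismatches between registered and diary-derived strata.

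**Cost:** SAP wording and model statements, with no new data collection. The baseline daily values must be derived for (a). Convergence is the small risk in (b), and (c) needs a little more programming. Moving daily duration from ANCOVA/ANOVA to MMRM, and stratifying the day-count tests if that is adopted, departs from Protocol 14.3.2.2. It should be recorded in SAP section 10, which currently lists no changes.

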8.3 Safety Assessments

Safety assessments of DBT period data and DBE period will be made on the SAF1 and SAF2 populations, resepectively. All data will be listed.

8.3.1 Adverse Events

The TEAEs are summarized for subjects with at least one TEAE, at least one treatment emergent adverse event related to study drug, at least one serious TEAE, at least one serious treatment emergent adverse event related to study drug, at least one TEAE leading to drug withdrawal, at least one treatment emergent adverse event related to study drug leading to drug withdrawal, at least one hepatic AE, at least one Adverse Events of Special Interest (AESI) and fatal TEAE. These TEAEs are summarized for subjects by region (North America, Europe, Japan, Australia) as well.

The frequency and incidence of TEAEs will be summarized by System Organ Class (SOC) and Preferred Term (PT) by treatment and overall. For this table, SOC is sorted by International order; then within SOC, PT is sorted by descending counts under MT-7117 combined total group, then descending counts under MT-7117 [REDACTED] group, then descending counts under MT-7117 [REDACTED] group, then descending counts under Placebo group, then alphabetic order for PTs with the same count.

The AE summaries will be presented for the following:

- TEAEs by SOC and PT
- TEAEs by SOC, PT and severity
- TEAEs by SOC, PT and relationship
- TEAEs by SOC, PT and region (North America, Europe, Japan, Australia)
- Treatment emergent adverse event related to study drugs by SOC and PT
- Treatment emergent adverse event related to study drugs by SOC, PT and severity
- Serious TEAEs by SOC and PT
- Serious treatment emergent adverse event related to study drug s by SOC and PT
- TEAEs leading to drug withdrawn by SOC and PT
- TEAEs by SOC and PT for TEAEs with frequency $\geq 3\%$ in MT-7117 any treatment groups
- Treatment Emergent Hepatic AEs by SOC and PT
(Note: Hepatice AE will be defined by SMQ Hepatic List in the appendix)
- AESI by SOC and PT
- TEAEs by SOC, PT and treatment duration
- TEAEs by SOC, PT, treatment duration and region (North America, Europe, Japan, Australia)
- Serious TEAEs by SOC, PT and treatment duration
- TEAEs by SOC and PT (Removing USUBJID: [REDACTED], [REDACTED], [REDACTED], [REDACTED])

For each of the summaries will be done at the subject level - multiple occurrences of the same event within a subject will be counted once in the summaries by SOC and PT; multiple occurrences of the same event within a subject will be counted once in the maximum intensity category (severe > moderate > mild) and/or maximum drug relationship category (reasonable possibility, no reasonable possibility). If intensity or relationship is found to be missing the most severe occurrence will be imputed for that particular summary.

All AEs for each subject, including multiple occurrences of the same event, will be listed. Deaths that occur during the study will be listed in a data listing. The data listings for serious TEAE and TEAE leading to drug withdrawn will be generated as well.

8.3.2 Laboratory Tests

Absolute values and changes from baseline will be summarized for the following laboratory tests parameters. For Haemoglobin, Haematocrit, Red Blood Cell, MCV, Alkaline phosphatase, Aspartate aminotransferase, Alanine aminotransferase, Gamma glutamyl transpeptidase and Bilirubin (direct and total), absolute values and changes from baseline will be summarized by region (North America, Europe, Japan, Australia). Standard Unit will be used for the summary.

Laboratory Test	Parameters
Hematology	Haemoglobin, Haematocrit, Red Blood Cell, Platelet count, MCV, MCH, MCHC, White blood cell count and differential
Biochemistry	Alkaline phosphatase, Aspartate aminotransferase, Alanine aminotransferase, Gamma glutamyl transpeptidase, Potassium Sodium, Chloride, Inorganic phosphate, Glucose, Bilirubin (direct and total), Blood urea nitrogen, Cholesterol, Triglycerides, High density lipoprotein cholesterol, Low density lipoprotein cholesterol, Protein (total), Albumin, Creatine kinase, Creatinine, Ferritin, Vitamin D
Coagulation	PT, INR, aPTT
Urinalysis	Specific gravity, pH, protein, glucose, ketones, urobilinogen, blood Microscopic examination ^a

^aPerformed only if required, based on urinalysis results

Shift table of clinically relevant categories will be presented for the following laboratory tests parameters. The categories will be Low, Normal and High for Hematology, Biochemistry, Urinalysis and Coagulation, and Normal and Abnormal for Urinalysis (Qualitative Value).

A shift table of the number and percentage will be provided for subjects who had any post baseline maximum value at any time during the treatment period and met the liver function tests (AST, ALT and Total bilirubin) criteria of the pre-defined limit for the maximum value.

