12.3.1 Management and Evaluation of Hepatic Adverse Events of Special Interest

Hepatic AESIs should be treated per the Investigator's approved standard of care and assessed for possible alternative etiology(ies). Hepatic AESIs will be followed clinically until resolution.

Subjects meeting the laboratory criteria of ALT/AST and total bilirubin defined in Section 12.3 (with or without alternative etiology), regardless of whether clinically significant or not, should be reported as a hepatic AE of special interest (AESI). The abnormal laboratory values should be confirmed by repeated measurements as soon as possible (i.e., within 7 days after the first observation) at local or central laboratory. Regarding any subject who meets the AESI criteria, the Investigator should discuss with the Sponsor Medical Monitor about the determination of etiology and the possibility for suspension of dosing. Resumption of dosing will be considered based on the discussion with the Sponsor Medical Monitor and Investigator.

All hepatic AESIs (including event management and evaluation) will be recorded and reported similar to SAEs as described in Section 12.8.

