The number of subjects with post-baseline assessments $\geq 2 \times$ ULN and $\geq 3 \times$ ULN and so on will be calculated for ALT, AST, GGT, ALP, direct and total bilirubin and summarized by treatment group for each post-baseline visit.

The figure of mean (or median) and standard error value of ALT, AST, total bilirubin and alkaline phosphatase by visit will be plotted.

Vital signs and electrocardiogram data

Vital signs and 12-lead ECG variables and changes from baseline will be descriptively summarized at each visit by treatment group.

The baseline for the vital sign parameters and 12-lead ECG measurements will be the last valid assessment obtained on Day 1 prior to the administration of double-blind treatment period.

For ECGs, number and percentage of subjects meeting the criteria listed below will be presented in tables:

- Baseline Corrected QT interval (QTc) <450 msec and >500 msec at EOT
- Baseline QTc <450 msec and 500 msec \geq QTc > 480 msec at EOT
- Baseline QTc <450 msec and 480 msec \geq QTc > 450 msec at EOT
- Increase from baseline at EOT in QTc > 30 msec
- Increase from baseline at EOT in QTc > 60 msec

These criteria will be applied to both Corrected QT interval using Bazett's formula (QTcB) and Corrected QT interval using Fridericia's formula (QTcF).

Physical examination and Nevi evaluation

Physical examination data will be summarized descriptively (number and percentage of the subjects) in tables by treatment and time point.

Nevi appearance will be summarized descriptively (number and percentage of the subjects) in tables by treatment and analysis visit for subjects' suspicious nevi found.

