1 INTRODUCTION

This statistical analysis plan (SAP) is based on the final global master protocol version 4.1 dated 9AUG2021, the final Japan specific protocol (v4.2) dated 24 August 2021, and the final Norway specific protocol (v4.3) dated 24 August 2021, and the final Germany specific protocol (v4.4) dated 24 August 2021 and , and the final Canada specific protocol (v4.5) dated 24 August 2021. The plan covers statistical analysis, tabulations, and listings of the study data to assess the efficacy, safety, and PK of [REDACTED] and [REDACTED] doses of MT-7117 compared to placebo.

Any statistical analysis details described in this document supersede any description of statistical analysis in the protocol.

The SAP is prepared by MTD A and MTPC data science and reviewed by MTD A clinical study team and MTPC data science following GLB-BST-SOP002 ver.7. The statistical analyses and production of the outputs described in the SAP will be conducted and QCed by [REDACTED]
[REDACTED] using SAS version 9.4 or higher. The final analyses and outputs will be approved by MTPC/MTD A Data Science.

This SAP has been approved and signed as Version 1.0 and Version 1.1 for FDA SAP communication. Version 2.0 will be finalized for the Primary Week 26 analysis prior to Week 26 database lock, and Version 3.0 will be finalized for the final analysis prior to the final database lock.

The analysis plan for the PPKPD will be described in a separate document and the results will be separately reported.

For the qualitative exit interview questionnaire, the analysis plan , the dataset and the results will be separately created and reported.

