6 STATISTICAL CONSIDERATIONS

6.1 Descriptive Statistics

Continuous data will be summarized descriptively using the number in the analysis set (N), the number of observations (n), mean, standard deviation (SD), median, minimum and maximum. Categorical data will be summarized using frequency counts and percentages. The denominator for the percentages will be the total number of subjects in the treatment group and analysis population being presented, unless otherwise specified (e.g. on some occasions, percentages may be calculated out of the total number of subjects with available data at a particular visit and/or time point).

Unless otherwise specified, all data will be summarized by analysis visits and treatment group.

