7.2.3.3 Laboratory Tests

(1) Criteria for pre-defined limit

Liver function:

- ALT $\geq 10 \times \text{ULN}$
- $8 \times \text{ULN} \leq \text{ALT} < 10 \times \text{ULN}$
- $5 \times \text{ULN} \leq \text{ALT} < 8 \times \text{ULN}$
- $3 \times \text{ULN} \leq \text{ALT} < 5 \times \text{ULN}$
- $1 \times \text{ULN} \leq \text{ALT} < 3 \times \text{ULN}$

The above same criteria will be applied to AST.

- Total Bilirubin $\geq 2 \times \text{ULN}$
- $1 \times \text{ULN} \leq \text{Total Bilirubin} < 2 \times \text{ULN}$

7.2.3.4 12-Lead ECG

(1) Criteria for pre-defined limit

12-lead ECG:

- Baseline QTc $< 450 \text{ msec}$ and $> 500 \text{ msec}$ at any post baseline
- Baseline QTc $< 450 \text{ msec}$ and $500 \text{ msec} \geq \text{QTc} > 480 \text{ msec}$ at any post baseline
- Baseline QTc $< 450 \text{ msec}$ and $480 \text{ msec} \geq \text{QTc} > 450 \text{ msec}$ at any post baseline
- Increase from baseline in QTc $> 30 \text{ msec}$, 60msec at any post baseline

The above same criteria will be applied to QTcF and QTcB.

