10 CHANGE FROM THE PROTOCOL

There are currently no changes to analysis from protocol.

[figure not shown]
[figure not shown]

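### The protocol's by-visit ULN-multiple counts for six liver markers are missing from the readable SAP, which has one period-maximum table for three markers and declares no change

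*SAP*

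**What the plan says.** Protocol 14.3.3, under safety laboratory tests, plans the number of subjects at ≥2× ULN, at ≥3× ULN, and at an open-ended series of higher multiples. These numbers "will be calculated for ALT, AST, GGT, ALP, direct and total bilirubin and summarized by treatment group for each post-baseline visit".

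SAP 7.2.3.3 sets the ULN limits. ALT has five bands: 1× to <3×, 3× to <5×, 5× to <8×, 8× to <10×, and ≥10×. For the second transaminase it adds: "The above same criteria will be applied to AST". Total bilirubin has two bands, 1× to <2× and ≥2×. GGT, ALP and direct bilirubin have none.

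SAP 8.3.2 uses these bands once, in a shift table for subjects with a post-baseline maximum value "at any time during the treatment period and met the liver function tests (AST, ALT and Total bilirubin) criteria of the pre-defined limit". The other categorical laboratory output is a general shift table: "The categories will be Low, Normal and High for Hematology, Biochemistry, Urinalysis and Coagulation".

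On the relation between the documents, SAP 10 says "There are currently no changes to analysis from protocol", and SAP 1 says "Any statistical analysis details described in this document supersede any description of statistical analysis in the protocol".

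**The concern.** Protocol 7.3 ties liver monitoring at every planned visit to the drug's potential to raise these markers. Protocol 7.2 explains the frequent testing by hepatic marker changes in rats and monkeys and by transaminase elevations in a Phase 1 study. Counts by arm and visit at fixed ULN multiples show how many subjects crossed each level and when. The three markers with no bands include ALP, GGT and direct bilirubin, which speak to cholestatic change, in a disease where Protocol 5 says prognosis depends on the evolution of hepatic disease.

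The bands that remain are also coarse at the lower end. Protocol 8.4 admits subjects with AST, ALT or ALP below 3× ULN. A subject whose ALT rises from 1.1× to 2.9× ULN stays in one SAP band, whereas the protocol's ≥2× cut would show the move.

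The second problem is the declaration in SAP 10. The SAP overrides the protocol only for details that it describes, and it does not describe the by-visit counts. A reader therefore cannot tell whether the protocol's table is still due or has been withdrawn.

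**Working it through.** The documents state no figure to reproduce. The check sets the protocol's named counts against the SAP's bands.

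**Inputs.** Protocol 14.3.3: 6 markers and 2 named cuts (≥2×, ≥3×), by arm and visit. SAP 7.2.3.3: the bands listed above. SAP 8.3.2: one table on the period maximum.

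**Named counts per arm and visit.** 6 markers × 2 cuts = 12, before any higher multiple.

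**What the SAP bands can yield.**

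| Marker | ≥2× ULN | ≥3× ULN |
|---|---|---|
| ALT | No: 2× lies inside the 1× to <3× band | Yes: sum of the four bands from 3× upward |
| AST | No: same reason | Yes: same sum |
| Total bilirubin | Yes: top band | No: 3× lies inside the open ≥2× band |
| GGT | No band | No band |
| ALP | No band | No band |
| Direct bilirubin | No band | No band |

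Derivable: ALT ≥3×, AST ≥3×, total bilirubin ≥2× = 3 of 12. Not derivable: ALT ≥2×, AST ≥2×, total bilirubin ≥3× (3), plus three markers × 2 cuts (6) = 9 of 12. Check: 3 + 9 = 12.

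**By visit.** The three derivable counts each come from a single maximum over the period, so 0 of 12 are available by visit.

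**Size of the missing table.** On the global schedule in SAP 9.3, liver markers are reported in DBT at Weeks 2, 4, 8, 12 and 26 and at follow-up, which is 6 visits. 6 × 12 = 72 cells per arm at the two named cuts, leaving out country-specific visits and the last-observation end-of-treatment row. This describes the size of one table and does not measure the consequence of its absence.

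**Does another SAP rule restore the counts?** SAP 6.1 makes summaries by visit and treatment group the default, but only unless otherwise specified. The liver table specifies a maximum over the period, and a by-visit default cannot create ULN cuts for markers that have none. SAP 1 settles which document prevails where both speak. It does not make the statement in SAP 10 true.

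**The case against.** The strongest reply is that the gap is one of presentation.

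- SAP 8.3 lists all data, and SAP 8 orders listings by treatment, subject and visit. Protocol 14.3.3 has high values flagged. With about 61 subjects per arm, such listings can be read.
- The by-visit descriptive statistics include "mean, standard deviation (SD), median, minimum and maximum", so a high value in any arm is visible at its visit. SAP 8.3.2 repeats the summaries by region for all six markers.
- The hepatic term list in SAP 14.2 includes increased GGT, ALP and conjugated bilirubin, so clinically significant rises recorded as AEs reach the hepatic TEAE table. AESIs are tabulated, and TEAEs are also shown by treatment duration.
- The SAP's cuts at 3×, 5× and 8× for transaminases and 2× for bilirubin correspond to the numeric AESI and withdrawal limits in Protocol 12.3 and 8.5. A maximum at any time can also catch an off-schedule peak that a by-visit table would miss, because SAP 7.3 keeps only the value nearest the nominal day.
- Protocol 7.2 reports transaminase elevations of 17% on both drug and placebo in Phase 1, and comparable hepatic findings in Phase 2.

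Most of this stands, and it sets the level of the concern. It does not remove it. A group maximum does not count subjects. The High category merges a value just above ULN with one several times ULN. Listings are not a comparison between arms. The numeric AESI limits use only ALT, AST and total bilirubin; the other three markers enter through judgement or a dosing interruption or discontinuation. The merits of the maximum table are a reason to keep it, not to drop the by-visit counts unannounced.

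A reader might infer more than the documents support, in three ways:

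- That the same counts were dropped for the extension. Protocol 14 leaves extension endpoints and methods to the final analysis SAP, so no definite number was promised there.
- That hepatic data are lost or a signal is hidden. The outputs above show otherwise.
- That follow-up values are barred from the maximum table. SAP 8.3.2 does not define the treatment period, and SAP 7.1 assigns follow-up data to the DBT analysis, so there is no stated rule.

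**Conclusion.** The concern holds for the DBT period, as a minor point. The readable SAP replaces a planned by-visit table for six markers with one maximum-value table for three. Only 3 of the 12 named counts can be derived from the SAP's bands, and none by visit. SAP 10 is therefore inaccurate on the readable text. No efficacy result, type I error rate or collected data point is affected; what is missing is a tabulated safety count.

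The conclusion assumes that no relevant table sits in text that cannot be read. SAP Section 13 is redacted, title included, which keeps confidence moderate. The figure of 12 counts uses only the two multiples that the protocol names. The protocol leaves anything above 3× open, so the SAP was free to choose those higher cuts.

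**What to change.** Add to SAP 8.3.2 one DBT table with the number of subjects at ≥2×, ≥3× and higher ULN multiples for ALT, AST, GGT, ALP, direct and total bilirubin, by arm at each post-baseline visit. Show the number of subjects with data per arm at each visit.

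In SAP 7.2.3.3, add a 2× cut for ALT and AST, a 3× cut for total bilirubin, and 2× and 3× cuts for GGT, ALP and direct bilirubin.

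Keep the maximum-value table, since it catches off-schedule peaks, and say whether it includes follow-up values. If any planned count is to be dropped, say so in SAP 10 and give the reason.

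The cost is one descriptive table from data already collected. The number with data matters most at the DBT follow-up visit, where subjects who enter the extension do not contribute.
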